6.8 Diagnosis and Management of Essential Fatty Acid Deficiency (EFAD)

EFAD will be suspected in all patients with abnormal plasma liver enzymes tests or any clinical signs of EFAD. The diagnosis will be confirmed by the planned FA profile analyses (see Appendix 1, Schedule of Events Table).

The Holman Index will be used for the diagnosis and management of EFAD.

The Holman Index, also called plasma triene:tetraene (T:T) ratio, is the ratio of the level of eicosatrienoic acid (Mead acid, n-9 FA) and the level of ARA (n-6 FA).

6.8.1 Holman Index < 0.2

Patients with a Holman Index of <0.2 have normal EFA status and will be followed for possible development of EFAD as defined in the study protocol.

6.8.2 Index between 0.2 and 0.4

Patients with a Holman Index of 0.2-0.4 are considered to be at risk for EFAD. Values in this range are indeterminate and may be seen in patients with adequate LA intake to prevent EFAD or in patients with low LA intake that are evolving toward EFAD.

The management of these patients includes first the assessment for clinical features of EFAD (dermatitis, diarrhea, perianal irritation, growth and development failure, recurrent infections, irritability, and/or poor wound healing).

Second, it implies checking if the plasma ARA levels are within normal range and that the unblinded pharmacist preparing the ILE determine if LA intake is adequate (See Section 6.8.5 Calculating LA Intake from ILE).

- If no clinical features are present:
 - If the ARA levels are within normal range with LA intake within the normal range (1-4% of the total energy intake), continue to follow the patient and check FA levels and Holman Index regularly (approximately every 15 days) till the Holman Index is normalized. The investigator and the patient may remain blinded.
- If the ARA level is low, increase LA intake even if in the normal range (1-4% of total energy intake). For example, if the level of LA intake is less than normal requirement (<1% of total energy intake), lipid intake will be increased to supply LA within the normal range (1-4% of total energy intake). If the patient is receiving a LA intake in the low normal range (1-2% of energy intake), it needs to be increased >2% of energy intake. If the patient is receiving a LA intake in the high normal range (3-4% of energy intake), it needs to be increased >4% of energy intake. The amount of the increase in LA intake should be determined by the clinician considering the clinical state of the patient and the safety of increasing the lipid intake. The monitoring of LA and ARA levels Holman Index and clinical features will persist regularly (every 15 days) till the Holman Index is normalized.
- If there are clinical features, increase LA intake even if in the normal range. For example, if the level of LA intake is less than normal requirement (<1% of total energy intake), lipid intake will be increased to supply LA within the normal range (1-4 % of total energy intake). If the patient is receiving a LA intake in the low normal range (1-2% of energy intake), it needs to be increased >2% of energy intake. If the patient is receiving a LA intake in the high normal range (3-4% of energy intake), it needs to be increased >4% of energy intake. The amount of the increase in LA intake should be determined by the clinician considering the clinical state of the patient and the safety of increasing LA intake. The monitoring of LA and ARA levels, Holman Index and clinical features will persist regularly (approximately every 15 days) until the Holman Index is normalized and clinical features disappear.

6.8.3 Holman Index >0.4

Patients with Holman index >0.4 will be considered as biochemical EFAD. It will be confirmed in the context of low LA, low ARA, and high eicosatrienoic acid (Mead acid).

Clinical EFAD is diagnosed in the presence of any clinical features of EFAD (dermatitis, diarrhea, perianal irritation, growth and development failure, recurrent infections, irritability, and/or poor wound healing).

The management of these patients includes the assessment, the record, and the increase of LA intakes until the Holman Index normalizes and clinical features, if present, disappear.

The daily monitoring of LA intakes, and the approximately every 15 day monitoring of LA and ARA levels and Holman Index will persist until the Holman Index normalizes and clinical features disappear. If the Holman Index does not reduce to <0.4 or if it continues to increase, lipid intake will be further increased. The amount of the increase in LA intake should be determined by the clinician considering the clinical state of the patient and the safety of increasing the total lipid intake.

Some patients may have higher requirements for EFAs due to an underlying disease (e.g. high demand for growth and wound healing). Total parenteral lipid intake should usually remain below the maximum intake (Table 4, Dosing Schedule), which is an amount that is normally adequate for prevention of EFAD in all patients. The patient should receive the increased LA intake for at least 1 week prior to repeating the FA profile with the Holman Index assessments to allow time for the physiologic effects of the FA to occur.

When EFAD persists despite maximal lipid intake, the ILE should be unblinded. If the patient is receiving Clinolipid, the patient should be switched to Intralipid to allow for greater delivery of LA.

Additional LA intakes may be supplied via intravenous and/or enteral/oral routes.

If severe hypertriglyceridemia (triglycerides >400 mg/dL) develops, the cause should be investigated. If it is determined to be related to the ILE, lipid intake may be adjusted using the ILE with the higher relative content of LA.

If direct bilirubin increases above 2.5 mg/dL suggestive of cholestasis, a reduction of total lipid intake may be considered while continuing to provide adequate LA. The adequacy of LA intake needs to be confirmed by the unblinded pharmacist(s).

6.8.4 Holman Index >0.4 at baseline

Some study patients (especially premature infants) may demonstrate FA profile and Holman index compatible with EFAD at baseline due to their limited fat stores. The treatment for these infants is to administer EFA via ILE as part of their PN as described in Table 4, Dosing Schedule and being sure to reach the maintenance dosage. Infants with EFAD at baseline are to be followed regularly (approximately every 15 days) while receiving ILE per study protocol for improvement in their FA profile and Holman Index.

• If the Holman Index does not decrease with lipid administration in accordance with Table 4, Dosing Schedule, the patient may have greater than normal

requirements for EFA and the LA intake should be increased to the maximum dosage according to Table 4, Dosing Schedule and at the investigator's discretion.

- If the patient still does not respond, the investigator will be unblinded to determine if the patient is receiving Clinolipid or Intralipid. If the patient is receiving Clinolipid, the patient should be switched to Intralipid (as Intralipid contains a higher concentration of LA than Clinolipid).
- If the patient does not respond to Intralipid at maximal lipid dosage, consider increasing the LA intake with an enteral/oral source of LA or some additional intravenous Intralipid intakes.

6.8.5 Calculating Linoleic Acid (LA) Intake from Intravenous Lipid Emulsion (ILE)

Clinolipid contains approximately 18.6% LA while Intralipid contains approximately 54.7% LA. Since both are 20% ILE (20 g/dL, 0.2 g/mL, 2 kcal/ml), the content of LA is approximately 0.11 g/mL for Intralipid (1.1 kcal/ml from LA) and 0.04 g/mL for Clinolipid (0.4 kcal/ml from LA) (Table 6).

Content	20% Intralipid	20% Clinolipid
Lipid, g/ml	0.2	0.2
Energy, kcal/ml	2	2
Linoleic acid, g/ml	0.11	0.04
Linoleic acid, kcal/ml	1.1	0.4

Table 6. Intralipid and Clinolipid Linoleic Acid Content

Sample Calculation:

If a 2 kg patient receives 16 mL of Intralipid per day, the patient receives 8 ml/kg/day of Intralipid. It corresponds to 1.6 g/kg/day of lipid and 0.88 g/kg/day of LA. The energy part of LA is 8.8 kcal/kg/day. If the total energy intake is 100 kcal/kg/day, it means that 8.8% of the energy intake comes from LA.

If a 2 kg patient receives 16 mL of Clinolipid per day, the patient receives 8 ml/kg/day of Clinolipid. It corresponds to 1.6 g/kg/day of lipid and 0.32 g/kg/day of LA. The energy part of LA is 3.2 kcal/kg/day. If the total energy intake is 100 kcal/kg/day, it means that 3.2% of the energy intake comes from LA.

The LA intake that normally prevents EFAD is 1-4% of total energy intake. The unblinded pharmacist determines if the patient has adequate LA intake for prevention of EFAD. The pharmacist communicates to the patient's nutrition clinician according to the protocol (see Sections 6.8.2, 6.8.3 and 6.8.4.).

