5.1.1 Clinolipid (lipid injectable emulsion, US Pharmacopeia) 20% - Investigational Product

Clinolipid is a sterile, non-pyrogenic ILE. Clinolipid contains a mixture of refined OO and refined SO in an approximate ratio of 4:1 (OO:SO). The lipid content is 0.20 g/mL. In Clinolipid, the mean composition of LA (n-6 EFA) is 35.8 mg/mL (range 27.6 to 44.0 mL) and ALA (n-3 EFA) is 4.7 mg/mL (range 1.0 to 8.4 mg/mL). The phospholipids provide 470 mg or 15 mmol of phosphorus per liter.

The total energy content, including fat, phospholipids, and glycerin is 2000 kcal/L.

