5.1.2 Intralipid 20% (lipid injectable emulsion, USP) – Active Control

Intralipid 20% (lipid injectable emulsion, USP) is the SOC 100% SO-based ILE. The lipid content of Intralipid 20% is 0.20 g/mL, with a LA content of 54.7% (approximately 0.11 g/ml).

The total energy content, including fat, phospholipids, and glycerin is 2000 kcal/L.

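### The linoleic acid (LA) intake calculation carries a rounded 0.04 g/mL for Clinolipid, 7.5% to 11.7% above the protocol's other two figures, against about 0.5% for Intralipid

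*Protocol*

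**What the plan says.** Three LA contents for Clinolipid can be read from the protocol.

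- Section 5.1.1, the product description: "the mean composition of LA (n-6 EFA) is 35.8 mg/mL (range 27.6 to 44.0 mL"). The range is printed without the mg; I read it as mg/mL, which gives 0.0358 g/mL (0.0276 to 0.0440).
- Section 6.8.5, first sentence: "Clinolipid contains approximately 18.6% LA while Intralipid contains approximately 54.7% LA". Both products are described as holding 0.2 g of lipid per mL, so 18.6% implies 0.0372 g/mL.
- Section 6.8.5 text, Table 6 and the sample calculation: "0.04 g/mL for Clinolipid (0.4 kcal/ml from LA").

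Intralipid is consistent. Section 5.1.2 describes it "with a LA content of 54.7% (approximately 0.11 g/ml"), and Section 6.8.5 uses the same values.

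The sample calculation takes 8 mL/kg/day of Clinolipid at 100 kcal/kg/day and concludes "it means that 3.2% of the energy intake comes from LA". Section 6.8.5 sets the result against a range of 1% to 4% of total energy. It has the unblinded pharmacist make that judgement and pass it to the clinician under Sections 6.8.2 to 6.8.4. Section 6.8.2 works with finer bands: below 1%, 1% to 2%, and 3% to 4%.

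**The concern.** Rounding to two decimals costs little at 0.1094 g/mL and much more at 0.0372 g/mL. Both products are rounded up, but the relative error is material only for Clinolipid. That is the product whose lower LA supply the Introduction names as a possible concern in children, especially premature infants.

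The figure is operational. Section 6.8.2 makes part of the management depend on the calculated percentage, and Section 6.8.3 asks the pharmacist to confirm adequacy if total lipid is reduced. The bands are one or two percentage points wide, so a relative error of about a tenth can move a patient across an edge. Two pharmacists working from different sections of the same protocol could classify the same patient differently.

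**Working it through.** **Inputs.** LA shares 18.6% and 54.7%, lipid 0.2 g/mL, and the Table 6 values 0.04 and 0.11 g/mL (Section 6.8.5); Clinolipid mean 0.0358 g/mL (Section 5.1.1); example of 8 mL/kg/day at 100 kcal/kg/day (Section 6.8.5); for preterm infants, maintenance lipid of 2.5 to 3 g/kg/day (Table 4) and target energy of 90 to 120 kcal/kg/day (Table 3).

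**1. Reproduce the plan's figures.** LA content = LA share × 0.2.
- Clinolipid: 0.186 × 0.2 = 0.0372, rounded to 0.04.
- Intralipid: 0.547 × 0.2 = 0.1094, rounded to 0.11.
- Implied energy factor: 0.4/0.04 = 1.1/0.11 = 10 kcal/g.
- Example: 8 × 0.04 = 0.32 g/kg/day; × 10 = 3.2 kcal/kg/day; 3.2/100 = 3.2%.

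The published example reproduces, but only with the rounded content.

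**2. Check the example against its own section.** 8 mL/kg is 1.6 g/kg of lipid. LA is then 0.32/1.6 = 20.0% of lipid, against the stated 18.6%. For Intralipid it is 0.88/1.6 = 55.0%, against 54.7%.

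**3. Size of the overstatement** (value used ÷ reference − 1).
- Clinolipid against 18.6%: 0.04/0.0372 − 1 = +7.5%.
- Clinolipid against the Section 5.1.1 mean: 0.04/0.0358 − 1 = +11.7%.
- Intralipid: 0.11/0.1094 − 1 = +0.5%.

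**4. Effect on the calculated percentage of energy**, keeping the protocol's 10 kcal/g throughout. Formula: (lipid g/kg ÷ 0.2) × LA content × 10 ÷ energy.

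| Case | 0.04 (Table 6) | 0.0372 (18.6%) | 0.0358 (Section 5.1.1) |
|---|---|---|---|
| Worked example, 1.6 g/kg, 100 kcal/kg | 3.20% | 2.98% | 2.86% |
| Maintenance, 2.5 g/kg, 120 kcal/kg | 12.5 × 0.4/120 = 4.17% | 12.5 × 0.372/120 = 3.88% | 12.5 × 0.358/120 = 3.73% |

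The second case pairs the lower end of preterm maintenance with the upper end of the preterm energy target. The same case for Intralipid gives 12.5 × 1.1/120 = 11.46% against 12.5 × 1.094/120 = 11.40%, well away from any band edge.

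**5. Which bands are crossed.** The worked example leaves the 3% to 4% band for the 2% to 3% interval, which the examples in Section 6.8.2 do not address. The maintenance case moves from above 4% into the 3% to 4% band. The first shift takes the patient out of a band for which Section 6.8.2, when ARA is low or clinical features are present, calls for an increase above 4%. The second puts the patient into that band. The error therefore does not push in a single direction.

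**The case against.** The best defence is that Section 6.8.5 says its contents are approximate, that 0.04 is a correct two-decimal rounding of its own 18.6%, and that 0.04 g/mL lies inside the Section 5.1.1 range. All of that is true, and it makes this a rounding inconsistency about the mean, not an impossible value. It does not explain why one protocol should yield three contents for a figure that feeds a banded decision.

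The defence also limits the consequence. With a Holman Index of 0.2 to 0.4, low ARA or clinical features lead to more LA even when calculated intake is in the normal range (Section 6.8.2). Above 0.4, intake is raised whatever the calculation shows (Section 6.8.3). Calculated adequacy settles whether to act mainly when ARA is normal and no clinical features are present, and those patients are rechecked about every 15 days.

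A reader might infer more than the documents support:

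- **An overstatement of 45%.** This compares 0.04 with the lower limit (0.04/0.0276). At the upper limit, 0.04 understates LA by 9% (0.04/0.0440 − 1). The range does not support a one-sided headline.
- **Inadequate intake read as adequate at the 1% edge.** Reading 0.895% as 1.0% at 100 kcal/kg takes 2.5 mL/kg, or 0.5 g/kg/day of lipid, half the Table 4 Day 1 figure. At the Day 1 figure and 120 kcal/kg/day, the Section 5.1.1 mean gives 5 × 0.358/120 = 1.49%. Only intake below the schedule comes near the edge. The protocol allows reductions but gives no figure for them.
- **Bias in the primary endpoint.** SAP Section 2.4.1.1 derives EFAD from the central laboratory's Holman Index, and the SAP calculates no LA intake. Any effect would be indirect, through lipid management, and the documents give no basis for sizing it.
- **An error in the energy factor.** Section 5.1.1 states: "The total energy content, including fat, phospholipids, and glycerin is 2000 kcal/L". One could therefore question 10 kcal/g for LA alone. The factor applies equally to both products, SAP Section 2.4.3.1 uses the same value for lipid, and a replacement would have to be assumed from outside the documents.

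**Conclusion.** The inconsistency stands and is modest in size. The adequacy calculation overstates Clinolipid LA by 7.5% if the 18.6% is the reference and by 11.7% if the Section 5.1.1 mean is, against 0.5% for Intralipid. The documents do not show which Clinolipid reference is better sourced, so the range is the finding. It is enough to change a patient's Section 6.8.2 band, both in the protocol's own example and at a dose and energy intake within Tables 3 and 4.

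This rests on reading the Section 5.1.1 range as mg/mL and on leaving the 10 kcal/g factor as the protocol has it. Individual lots may lie on either side of 0.04 g/mL. The consequence is confined to the LA-adequacy check and can run either way; it does not enter any planned analysis. It is worth correcting because the figure is used at the bedside and the correction is small.

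**What to change.** Reconcile Section 5.1.1, the Section 6.8.5 text, Table 6 and the sample calculation to one LA content per product. State the source and carry the value to at least three significant figures in both the g/mL and kcal/mL rows. Recompute the sample calculation from it. In the same edit, supply the missing mg in the Section 5.1.1 range.

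The cost is a change to one table and a few lines of protocol text, plus a notice to the site pharmacists so that any worksheet built from Table 6 is updated. The SAP needs no change. Nothing here proposes a dose, an adequacy threshold or an energy factor.

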6.9 Nutritional Intake

Prescribed and actual macronutrient intake (fluid, energy, protein, carbohydrates, and lipid) of both parenteral and enteral nutrition will be collected and recorded on a daily basis in the CRF from Baseline to end of study treatment for each of the treatment groups. See Appendix 1, Schedule of Events Table, for additional details.

Intravenous intakes (fluid, amino acid, dextrose/glucose, and lipid) from PN as well as any intravenous macronutrient additions to the PN solution will be collected and recorded as parenteral intakes.

For breast milk intake, the macronutrient content will be estimated from volume intakes using mean reference values in mature human milk (640 kcal, 12 g of protein, 67 g of carbohydrates, and 34 g of lipid per 1 Liter of milk).²³ When breastfeeding intakes cannot be measured, the best estimation (volume) of the investigator will be recorded. For commercial products including formula and human milk fortifiers, macronutrient intakes will be recorded from volume intake and calculated from manufacturer label. For oral food ingestion, energy and lipid intakes only will be recorded from best estimates.

6.10 Dispensing Study Treatment

Blinded study treatment will be provided to the pediatric/neonatal unit from the study site pharmacist(s). The pharmacist(s) will maintain accurate and complete records of study treatment dispensation. Study personnel in the pediatric/neonatal unit will administer study treatment to the patients intravenously using either a syringe pump or an infusion pump, as appropriate for the volume dispensed.

The amount of lipid emulsion (g/kg/day) delivered to the patient will be collected daily and recorded (volume, flow rate and infusion duration) for each administration of study treatment (See Section 6.9).

6.11 Concomitant Medications

Ongoing medications and nutritional supplements received by the patient and nursing mother (if applicable) will be recorded as concomitant medication once study treatment has been initiated. During treatment, concomitant medications and therapies (including dose, frequency, start and stop dates, and indication for use), will be recorded in the CRF by study site personnel on a daily basis.

During treatment, both patients' and nursing mothers' concomitant medications (as documented in the patient's chart) will be recorded.

6.12 Concomitant Procedures

Invasive concomitant procedures, including the below list, must be documented in the eCRF:

- Chest tube
- Surgical procedure
- Surgical central line placement
- Blood/platelet/fresh frozen plasma or other colloid infusion
- Pericardiocentesis, pleural or peritoneal tap
- Lumbar puncture

6.13 Adverse Events Assessments

An AE is any untoward medical occurrence in a patient or clinical investigational patient administered a study product, and that does not necessarily have a causal relationship with the treatment or drug. An AE can therefore be any unfavorable and unintended sign (including an abnormal laboratory function), symptom (e.g., rash, pain, discomfort, fever, dizziness, etc.), organ dysfunction (e.g., cardiovascular failure, pancreatitis, etc.), systemic illness (e.g., sepsis), or outcome of death temporally associated with the use of the study product, whether or not the event is considered associated with the study product.

Laboratory and vital sign abnormalities qualify as AEs if medical intervention is required to treat or address the abnormality, if the patient must be discontinued from the study due to the abnormality, or if the value exceeds specific limits defined by the SOC as qualifying it as an AE.

An elective procedure/surgery that occurs during the course of a study, but is being performed for a documented pre-existing condition and was pre-planned prior to study entry, will not qualify as an AE. If, however, the pre-existing condition unexpectedly deteriorates during the study requiring the procedure/surgery to be performed earlier than

planned, the condition for which the procedure/surgery is being performed will qualify as an AE.

In this study, AEs will be recorded in conjunction with the first study procedure (Screening). Adverse events occurring prior to the initiation of the first study procedure will be recorded as signs and symptoms in the patient's medical history. Adverse events occurring during Screening but prior to the administration of study treatment will be considered as unrelated to study treatment.

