7.1 Screening Period

After providing written IC, patients will enter the Screening Period. The Screening Period is defined as the period after the ICF is signed and dated until randomization. The maximum duration of this period is 3 days prior to dosing. Randomization is recommended within 24 hours of signing consent but must occur within 3 days of signing consent. If patient is not randomized within 24 hours of informed consent, patient should be started on SOC ILE on Day 1 of PN as per Table 4 and Section 5.3. Signing and dating of the ICF and the Screening visit may occur on the same day, if necessary; however, the ICF must be signed and dated before any Screening activities can be conducted.

The aim of the Screening Period is to determine the eligibility (inclusion/exclusion criteria) of patients for randomization.

Further assessments conducted during Screening include:

- Demographics
- Gestational age and birth weight for infants <1 years of age only
- Medical history (including diagnosis requiring PN)
- Physical examination, including weight and length or height (and head circumference for infants <1 year of age)
- Vital signs
- Laboratory evaluations including hematology and chemistry (refer to Appendix 1, Schedule of Events Table)
- Pregnancy test. Note: All female patients ≥12 years of age must have a negative urine human chorionic gonadotropin (hCG) pregnancy test at screening. For female patients <12 years of age, a urine hCG test at screening will be performed at the discretion of the investigator based on childbearing potential.
- Nutritional intakes
- Medication history
- Randomization to study treatment
- Adverse Events (AEs occurring during Screening but prior to administration of study treatment will be considered as unrelated to study treatment). Non-serious AEs during this time period will be collected as part of the medical history. Serious adverse events will need to be reported as per Section 6.13.7.2.

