2.5.1 Adverse Events

2.5.1.1 Derivation of Adverse Events

Adverse events (AEs) will be coded using MedDRA. They will be classified as follows:

Pre-treatment adverse event – An adverse event that starts between the date of signing the informed consent form (ICF) and the study treatment

Treatment-emergent adverse event (TEAE) – An adverse event that starts on or after the start of study treatment

Treatment-emergent adverse events of special interest (AESI) - The following are called out as AESIs in the protocol: catheter related infection, thrombophlebitis, dyspnea, cyanosis, allergic reactions, hyperlipemia, hypercoagulability, nausea, vomiting, headache, flushing, increase in temperature, sweating, sleepiness, pain in the chest and back, slight pressure over the eyes, dizziness, irritation at the site of infusion, hepatomegaly, splenomegaly, thrombocytopenia, leukopenia, and overloading syndrome (focal seizures, fever, leukocytosis, hepatomegaly, splenomegaly and shock). A blinded review of AEs will be conducted at the end of the study before unblinding to flag AESIs.

An adverse event will be considered related to study treatment if they respond 'Probably related' or 'Possibly related' to relationship to study treatment.

In case of incomplete information on study treatment or AE onset, events will be classified as treatment-emergent unless there is sufficient data to rule out the possibility that the event started after the start of study treatment.

If the severity of an adverse event is missing, then that adverse event will be classified as *severe*. If relationship of an adverse event is missing, then that adverse event will be classified as *probably related*.

The number of events per 100 patient days will be calculated as follows:

$$\frac{\text{Number of Total Events}}{\sum_{i=1}^{n} (\text{End Date of Treatment}_{i} - \text{Start Date of Treatment}_{i} + 1)}, \\100$$

where i represents each patient and n represents the total number of patients in the Safety Set for that treatment group.

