2.5.1.2 Analysis of Adverse Events

An AE overview summary table will be prepared to include the number of patients, the percentage of patients (%), and the number of events per 100 patient days by treatment group, for the following categories:

- 1. Any AE
- 2. Any treatment-emergent adverse event (TEAEs)

- 3. Treatment emergent non-serious AEs
- 4. Treatment-emergent serious AEs (SAEs)
- 5. Treatment-emergent AEs of special interest (AESIs)
- 6. Treatment-emergent AEs related to study treatment
- 7. Treatment-emergent SAEs related to study treatment
- 8. Treatment-emergent AEs leading to death

Additional listings and tables on the above categories (with the exception of #1) will be given by SOC and PT. Pre-treatment adverse events (those occurring between informed consent and treatment) will also be listed. For SAE listings, the seriousness criteria will be included in the listing.

The tables below will display the total number of patients, the percentage of patients (%), the number of events, the number of events per 100 patient days, system organ class (SOC), and preferred term by treatment group. Table summaries will be produced for:

- Treatment-emergent AEs by severity
- Treatment-emergent SAEs by severity
- Treatment-emergent AEs by relationship to study treatment
- Treatment-emergent SAEs by relationship to study treatment
- Treatment-emergent adverse events in ≥5% of patients (in either Clinolipid or Intralipid group)

Tables by preferred term and tables by system organ class (SOC) and preferred term will be sorted in descending order by the percentage of patients.

Adverse event listings will be sorted by patient ID and adverse event start date. They will include primary AE number, SOC, PT, verbatim term, adverse event start and end date and its duration, treatment date, relationship to study treatment, alternate causality, severity, action taken, seriousness, outcome, whether the event is ongoing, and whether AE led to discontinuation from study.

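### The protocol gives two rules for non-serious events during Screening, and the SAP's Any AE rate divides pre-treatment events by treatment days only, which overstates that one row

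*Protocol*

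**What the plan says.** **Protocol 6.13** sets the start of AE recording: "In this study, AEs will be recorded in conjunction with the first study procedure (Screening"). It sends only earlier events to medical history: "Adverse events occurring prior to the initiation of the first study procedure will be recorded as signs and symptoms in the patient's medical history". Note n to the schedule of events, in Protocol Appendix 1 and in SAP 1.4.5, repeats this second rule, and both schedules mark AE collection at Screening.

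**Protocol 7.1**, on the interval before study treatment, says: "Non-serious AEs during this time period will be collected as part of the medical history". Serious events are kept apart: "Serious adverse events will need to be reported as per Section 6.13.7.2". On the length of Screening it says: "The maximum duration of this period is 3 days prior to dosing".

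**SAP 2.5.1.1** defines a pre-treatment adverse event as "An adverse event that starts between the date of signing the informed consent form (ICF) and the study treatment". Seriousness does not enter the definition. Appendix 1 of the SAP plans a listing of all pre-treatment AEs (16.2.7.1.1) and another of serious ones (16.2.7.1.3).

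**SAP 2.5.1.2** specifies an overview table that gives, besides patient numbers and percentages, "the number of events per 100 patient days by treatment group, for the following categories". Row 1 is Any AE. Row 2 is "Any treatment-emergent adverse event (TEAEs"). The only rate formula, in SAP 2.5.1.1, divides total events by the sum over patients of the days from start to end of treatment, inclusive, and scales to 100 days. Protocol 9.6.3 also uses treatment exposure as the denominator.

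**The concern.** Take a non-serious event that begins after the first Screening procedure and before the first dose. Under 6.13 it is an AE; under 7.1 it is medical history. Neither document says which section governs. The choice decides whether the event appears in the Any AE row and the pre-treatment AE listing, or in the medical-history table.

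The second problem follows from the first. If such events are counted in the Any AE row, they add to the numerator of a rate whose denominator contains no pre-treatment time. The first line of the safety overview would then be too high as a rate per patient-day, by an amount that depends on how Screening events were filed. The trial is purely descriptive, so readers will take its reported rates at face value.

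**Working it through.** The documents state no AE rate, so there is no figure to reproduce. The check compares the texts and then applies the SAP's own formula.

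**Which rule the other sections follow.** Protocol 6.4 records clinically significant new or worsened conditions since Screening as AEs. Protocol 7.2.1 lists AEs as a Baseline procedure before dosing. SAP 2.1.1 treats as medical history only conditions already present when the patient is screened. Two SAP listings, one for all and one for serious pre-treatment AEs, would hold nearly the same events if 7.1 were followed. Section 7.1 is therefore the outlier on non-serious events.

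**Start points.** They are not uniform even without 7.1. Section 6.13 and note n start at the first study procedure. SAP 2.5.1.1 and the SAE reporting rule in Protocol 6.13.7.2 start at signing of consent.

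**What the Any AE row holds.** The SAP does not define it. It classifies AEs by timing only as pre-treatment or treatment-emergent, and lists Any AE separately from the treatment-emergent row. If row 1 excluded pre-treatment events, it would duplicate row 2. Inclusion is an inference from this.

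**Size.** Inputs: Screening of S days, at most 3 (Protocol 7.1), with randomization recommended within 24 hours of consent; treatment of T days, nominally 7 to 90 (Protocol 5.2). Assume a constant daily event rate λ before and during treatment.

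- Rate with all Screening events counted = λ(T + S)/T
- Treatment-emergent rate on the same days = λ
- Relative excess = S/T

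| Treatment days T | S = 1 | S = 3 |
|---|---|---|
| 7 | 1/7 = 14.3% | 3/7 = 42.9% |
| 15 | 1/15 = 6.7% | 3/15 = 20.0% |
| 30 | 1/30 = 3.3% | 3/30 = 10.0% |
| 90 | 1/90 = 1.1% | 3/90 = 3.3% |

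The rate is pooled, so for an arm S and T are the mean Screening and mean treatment days.

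If only serious Screening events are counted, as under 7.1, the excess is qS/T, where q is the serious share of events. The documents give no q. For an assumed 10% to 20% and S = 3, it is 4.3% to 8.6% at 7 days and 0.3% to 0.7% at 90 days.

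**Worked case.** Take 50 patients in an arm, 15 treatment days, 3 Screening days and an assumed 10 events per 100 patient-days.

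- Treatment days: 50 × 15 = 750, with 75 events on treatment
- Screening days: 50 × 3 = 150, with 15 events
- Any AE, all Screening events counted: 100 × 90/750 = 12.0
- Any AE, serious Screening events only: 100 × 76.5/750 = 10.2 to 100 × 78/750 = 10.4
- Treatment-emergent events only: 100 × 75/750 = 10.0
- Screening days added to the denominator: 100 × 90/900 = 10.0

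**The case against.** The strongest reply is that little depends on this row. Its content is inferred. Row 2 directly below gives the treatment-emergent rate, and SAP 2.5.1.2 leaves row 1 out of the further tables by system organ class and preferred term. The tables by severity, by relationship and for events in at least 5% of patients are all treatment-emergent. Protocol 6.13 deems pre-dose events unrelated to treatment, so related-event rows are untouched. All of this stands and limits the point to one row, the pre-treatment listings and medical history.

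A reader might infer four stronger things that the documents do not support.

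- **A distorted comparison between arms.** Common pre-treatment events would pull a rate ratio towards 1, but the SAP plans no AE rate ratio and no test. Randomization is stratified by site, so filing practice should affect both arms similarly.
- **Sites actually differing.** The text permits it, but conduct depends on CRF design and completion instructions, which are not in these documents.
- **43% as a typical excess.** It needs three Screening days and seven treatment days on average across an arm, with every Screening event counted.
- **Treatment-emergent rates as clean on-treatment rates.** Under Protocol 6.13.1, AEs can be collected for up to 30 days after the last dose, and the SAP's treatment-emergent definition has no end date. Those rows are free of pre-treatment events, but later events can still enter without added patient-days. That is a separate matter.

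**Conclusion.** The point holds and is minor. Sections 6.13 and 7.1 conflict on non-serious events between the first study procedure and the first dose, and the SAP's definition and listings do not fit 7.1. If the Any AE row includes pre-treatment events, as its place in the table implies, its rate is overstated whenever at least one is counted; with none, there is no excess.

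A plausible size is the one-day column of the table, given the recommendation to randomize within 24 hours; the three-day column is the upper end. Both rest on a constant event rate and on counting all Screening events. No planned inference depends on the row.

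**What to change.** **Protocol.** Choose one start point for AE recording, either the first study procedure or signing of consent. State it identically in 6.13, 7.1, Appendix 1 note n and the SAP, in line with the SAP 2.1.1 rule on conditions present at screening. Remove the 7.1 sentence on non-serious events. Removing it alone is not enough: 6.13 and Appendix 1 start at the first study procedure, whereas SAP 2.5.1.1 starts at consent.

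**SAP 2.5.1.2.** Define the Any AE row. Drop its rate per 100 patient-days, or compute that row's rate with person-time from the start of AE recording. Show pre-treatment AEs as a separate count.

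**Cost.** A few sentences of protocol and SAP text and one table row. Some Screening events may have to be moved from medical history to the AE form.
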